3.2 SECONDARY OUTCOMES

Physical activity levels in daily life using Actigraph GT3x activity monitor, quadriceps muscle strength through the quadriceps maximal voluntary contraction test (QMVCT), quality of life using IPF-specific version of the St George's Respiratory Questionnaire (SGRQ), anxiety and depression levels through the Hospital Anxiety and Depression Scale (HADS), dyspnoea through the Modified version of the Medical Research Council scale (mMRC). The number of patients using anti-fibrotic medication will also be assessed.

Additionally, we will explore impact in blood biomarkers associated with fibrosis selected from the ELMEN study that have been shown to be associated with disease

progression (Inc. but not restricted to PAI-1, VEGF-A, PDGF-AA, PDGF-BB, Cystatin-C, Angioprotein-1, HE4/WFDC-2) (21).

We will also assess if the patients who are in treatment with antifibrotic medicines have better results than those who are not in treatment with antifibrotic medicines. This will be done in an exploratory way, where at the end of the study we will compare statistically if those patients who had a prescription of antifibrotics had better results compared to those who did not have a prescription of these medicines.

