1. INTRODUCTION

1.1 BACKGROUND

Interstitial lung disease (ILD) is a diverse group of entities that cause damage to the lung parenchyma through varying degrees of inflammation and fibrosis. Fibrotic ILDs result in restrictive ventilatory physiology and impaired gas exchange, frequently leading

to exertional hypoxemia and functional limitation (1). These diseases have been classified into various groups: ILD of known cause such as occupational or environmental exposures including Pneumoconiosis and Hypersensitivity Pneumonitis, ILD associated to connective tissue diseases/vasculitis, idiopathic interstitial pneumonias including idiopathic pulmonary fibrosis (IPF) and nonspecific interstitial pneumonia (NSIP), granulomatous ILD such as sarcoidosis and other rare forms of ILD including lymphangiomyomatosis (2, 3, 4). Among all these diseases the most common is IPF whose number of deaths in the UK according to the data from the office of national statistics increased from 1.66 per 100,000 people in 1979 to 8.29 per 100,000 people in 2016 (5). The mechanisms of reduced exercise capacity in ILD are multi-factorial. Impaired gas exchange occurs as a result of destruction of the pulmonary capillary bed and thickening of the alveolar-capillary membrane, resulting in ventilation-perfusion mismatch and oxygen diffusion limitations. Circulatory limitation results from pulmonary capillary destruction and pulmonary vasoconstriction and leads to pulmonary hypertension and cardiac dysfunction in some patients. Ventilatory limitations to exercise may also occur, although these are not thought to be a major contributor in most patients (6, 7). Peripheral muscle dysfunction is also a key factor to exercise limitation. Patients who suffer from ILD tend to avoid activities that trigger dyspnoea and fatigue, consequently they reduce their levels of physical activity, which leads to physical deconditioning and increasing symptoms. Furthermore, treatment with corticosteroids and immunosuppressants, as well as systemic inflammation, may also negatively impact on peripheral muscle function in some patients with ILD (6, 7). Pulmonary rehabilitation is an evidence-based, multidisciplinary and comprehensive intervention for patients with chronic respiratory disease who are symptomatic and often have decreased daily life activities. PR programmes include exercise training - which is the cornerstone of PR and includes aerobic conditioning, strength and endurance training respiratory therapy, education, nutritional interventions, psychological and social support and behaviour modification techniques (8, 9, 10). PR can be performed in different places; such as hospital outpatient departments, community health centres and even at home, showing similar results. PR has demonstrated improvements in symptoms, exercise tolerance and quality of life in chronic respiratory diseases other than COPD, including ILD and pulmonary hypertension, despite differences in underlying pathophysiology among them. Nevertheless, there is much less evidence of these improvements and the mechanisms by which pulmonary rehabilitation might improve outcomes in ILD compared to COPD (6, 7). Despite this, guidelines for pulmonary rehabilitation recommend its use in patients with chronic respiratory disorders other than COPD. Emerging evidence suggests that pulmonary rehabilitation may result in meaningful short-term benefits in patients with ILD, mainly on exercise tolerance, muscle function, dyspnoea and quality of life. However, the magnitude of these benefits is smaller than those generally seen in COPD and its ongoing effects are not evident six months after training (7). This may reflect the challenges in providing pulmonary rehabilitation for conditions such as idiopathic pulmonary fibrosis (IPF) that can be rapidly progressive (11). Guidelines for clinical management ILD point out that more information is needed on the benefits of pulmonary rehabilitation for this group of patients (7, 12). The greater prevalence of exercise-induced hypoxia, pulmonary hypertension and arrhythmia compared with other chronic lung diseases in this patient population raises the possibility that response to exercise rehabilitation may also differ (6, 7). In turn, high flow nasal oxygen allows the delivery of a well humidified high flow of air with a mix of oxygen from 21 to 100% and also provides a low level of positive end-expiratory pressure (PEEP). This strategy can achieve higher values of oxygenation even in acutely ill patients with ILD (13, 14) and may

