4.8 RANDOMISATION

Following confirmation of eligibility by the CI or PI and signature of the informed consent, patients will be randomised using sealed letters to HIIT plus HFNO or HIIT plus nasal cannula. Patients will be sequentially randomised. Randomisation code and sealing of envelopes will be done by the research nurses and stored in a room at RIE and Royal

Victoria Infirmary accessible with a key. This will be done before any baseline procedures.

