4.12 DATA COLLECTION

The UK General Data Protection Regulation (GDPR) requires appropriate technical and organisational measures to be in place to implement the data protection principles effectively and safeguard individual rights. This is ‘data protection by design and by default’.

In essence, this means we will integrate or ‘bake in’ data protection into our processing activities and business practices, from the design stage right through the lifecycle.

4.12.1 Data to be collected:

- Weight
- Height
- Blood Test (blood biomarkers associated with the progression of the fibrosis)
- Blood Pressure
- QMVCT (Strength of the Quadriceps muscle measured in Newtons)
- mMRC (score of dyspnoea from 1 to 5)
- CPET (Maximum workload measured in watts)
- CWRCT (time or exercise tolerance measured in minutes)
- Physical activity levels in daily life (measured in steps)
- SGRQ (Score of this questionnaire that measures the QoL)
- HADS (Score of this questionnaire that measures anxiety and depression levels)

4.12.2 Time points for collection: these data will be collected during the baseline and post intervention appointment by the CI ([name]) and the PI ([name]) in Edinburgh and by [name] (Physiotherapist) in Newcastle.

4.12.3 Details of standardised tools to be used:

- Modified version of the Medical Research Council scale (mMRC): see appendix D.
- Saint George Respiratory Questionnaire (SGRQ): see appendix E.
- Hospital Anxiety Depression Scale (HADS): see appendix F.

4.12.4 Methods to maximise completeness of data: PI will call participants who have not returned questionnaires.

4.12.5 How will data be recorded Data will be recorded using both eCRF and pCRF.

4.12.6 Source Data Documentation: Source data is defined as all information in original records and certified copies of original records or clinical findings, observations, or other activities in a clinical study necessary for the reconstruction and evaluation of the study. Source data are contained in source documents.

Source documents are original documents, data and records where source data are recorded for the first time.

We will use the medical records from Trak to obtain information of the high resolution computed tomography (HRCT) of the thorax, echocardiograms, breathing tests including Spirometry, Lung volumes and DLCO.

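### The exploratory antifibrotic comparison in section 3.2 uses an undated, non-randomised exposure with no listed data item, and only unadjusted tests are stated for it

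*Protocol*

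**What the plan says.** Section 3.2 (secondary outcomes) first lists a count: "The number of patients using anti-fibrotic medication will also be assessed". It then asks whether "patients who are in treatment with antifibrotic medicines have better results than those who are not in treatment". The method follows: "This will be done in an exploratory way", and "at the end of the study we will compare statistically if those patients who had a prescription of antifibrotics had better results", with patients who had none as the reference group. No outcome is named for the word results, and neither description of exposure has a date.

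Section 4.8 randomises oxygen delivery only: "patients will be randomised using sealed letters to HIIT plus HFNO or HIIT plus nasal cannula". Section 6 gives a chi-squared test or Student's t-test for comparisons between groups, at p < 0.05 for every comparison. It has no term for arm, baseline value or any other covariate.

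The 11 items in section 4.12.1 run from weight to HADS and include no medication. Section 4.12.6 names the record sources: "We will use the medical records from Trak to obtain information of the high resolution computed tomography (HRCT) of the thorax", followed by echocardiograms and breathing tests. The schedule in section 4.11 has no medication row. Appendices A and B tell the operator to enter further details in the Patient History tab of the exercise-test software and give medication as one example.

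**The concern.** The comparison is between patients who were prescribed a medicine and patients who were not, in a trial that randomises something else. Three features of the text make its result hard to interpret.

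- **Exposure has no date.** A patient who starts an antifibrotic during the programme could be counted as a user, so group membership could depend on events after baseline.
- **The stated tests are unadjusted.** A difference between users and non-users would carry any difference in diagnosis and severity, and part of any HFNO effect if users happen to be unevenly split between arms.
- **No listed item supplies the exposure.** If it is not recorded with a date while patients are in the study, an analysis plan written later cannot restore it.

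At stake is one secondary statement, about whether antifibrotic users did better. The randomised comparison of endurance time does not depend on it.

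**Working it through.** **1. Figure to reproduce.** There is none. Section 6 says that no sample size was calculated and that about 30 patients are expected. The protocol gives no number of users, no outcome SD and no effect size.

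**2. The two descriptions of exposure, side by side.** They can classify the same patient differently:

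| Patient | In treatment, judged at baseline | Had a prescription, judged at analysis |
|---|---|---|
| On treatment throughout | user | user |
| Starts after baseline | non-user | user |
| Stopped before baseline | non-user | user, if any past prescription counts |
| Never prescribed | non-user | non-user |

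The columns are two permissible readings. The text chooses neither date.

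**3. Time in which status can change.** Sections 4.1 and 4.11 allow 1 to 30 days from the baseline visit to the first session, 8 weeks of training, and 8 to 38 days from the last session to the post visit.

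- Shortest: 1 + 8 × 7 + 8 = 65 days
- Longest: 30 + 8 × 7 + 38 = 124 days

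**4. Effect of a prognostic gap (illustration).** Assumptions: N = 30; m users; a medicine with no effect; users and non-users differing in prognosis by c SD; unadjusted two-sided t-test at 0.05 with 28 df (section 6 does not state sidedness). The noncentrality is c / √(1/m + 1/(30 − m)).

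For m = 10 and c = 0.5: √(1/10 + 1/20) = 0.387, and 0.5 / 0.387 = 1.29. The probability of p < 0.05 is 0.239.

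| Users / non-users | c = 0.25 | c = 0.5 | c = 0.8 | c = 1.0 | Difference detectable with 80% power, no confounding |
|---|---|---|---|---|---|
| 6 / 24 | 0.083 | 0.185 | 0.395 | 0.562 | 1.32 SD |
| 10 / 20 | 0.096 | 0.239 | 0.514 | 0.703 | 1.12 SD |
| 15 / 15 | 0.101 | 0.262 | 0.562 | 0.753 | 1.06 SD |

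Splits of 20/10 and 24/6 give the same values as 10/20 and 6/24. The protocol does not say how prescribing relates to diagnosis or severity, so the gap is an assumption. It is plausible because section 4.3 admits fibrosing lung disease on imaging without restricting diagnosis, with TLCO from 25% to 80% predicted.

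**5. Chance imbalance of arm (illustration).** Assume 15 patients per arm and use fixed before allocation. The number k of users in the HFNO arm is then hypergeometric, and the difference in HFNO share is k/m − (15 − k)/(30 − m). Its expectation is zero, because each group expects half its members in HFNO. For m = 10 its SD is 0.197.

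- Example: 7 of 10 users and 8 of 20 non-users in HFNO gives 0.70 − 0.40 = 0.30, so 30% of any true HFNO effect would appear as a user difference.
- An imbalance of 20 points or more, in either direction, has probability 0.25 (10/20), 0.47 (15/15) or 0.65 (6/24). For 10/20 this means 7 or more, or 3 or fewer, users in HFNO.

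**The case against.** The case on the other side is strong in several places, and most of it stands.

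- **Timing.** A reader might infer that status is taken at the end of the study. The text does not say so: those words date the comparison, not the prescription. Nor do the documents say that worsening disease leads to prescribing. Section 4.6 discontinues patients whose progression prevents participation, which narrows that route. What remains is that exposure has no date, so classification after baseline is possible, not certain.
- **Label.** The protocol already calls the analysis exploratory and does not itself claim a causal effect of the medicine.
- **Arm.** Section 3.2 is silent on arm, so pooling over arms is inferred from that silence and from the tests in section 6. A reader might call the comparison biased by arm. Arm is randomised, so for use fixed before allocation the expected imbalance is zero. The effect is added noise, not systematic bias.
- **Data.** A reader might conclude that medication is not collected. The exercise-test software has a place for it, and list 4.12.1 is not exhaustive: it omits demographics and adverse events, which the protocol collects elsewhere. The supportable statement is narrower. Antifibrotic use is not an item in the list, the named sources or the schedule, and the one entry route is general, with no date required.
- **Analysis plan.** Covariate adjustment for an exploratory contrast may stand in a statistical analysis plan that is not shown. That is fair for the model. It does not settle a dated exposure, which must be recorded while data are being collected.

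**Conclusion.** The point holds at low severity. Section 3.2 commits to a statistical comparison on an exposure that is not randomised, is described in two ways and has no date. The only tests in the protocol are unadjusted, and no listed data item supplies the exposure. Carried out as written, the result could include prescriptions started during the 65 to 124 days between assessments. It could not separate the medicine from diagnosis and severity, and it would carry noise from any chance imbalance of arm.

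The time window follows from the protocol. The percentages do not: they rest on assumed user counts (6 to 24 of 30), assumed prognostic gaps (0.25 to 1.0 SD), equal arms and a two-sided test. They show the order of size only. The documents do not support saying that the comparison is systematically biased by arm, that status is fixed at the end of the study, or that medication goes unrecorded. The primary analysis is unaffected.

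**What to change.** - **Section 3.2, exposure.** Use one definition: on antifibrotic treatment at randomisation. Report the number of users as a baseline characteristic by arm.
- **Section 4.12.1.** Add antifibrotic use with start and stop dates up to the post visit, taken from the medical records already consulted, and name this source in 4.12.6.
- **Section 3.2, analysis.** Name the outcomes meant by results. Replace the user versus non-user test with an estimate and 95% confidence interval from a model containing randomised arm and the baseline value of the outcome. Label it an exploratory association that remains confounded by diagnosis and severity. The model removes the noise from arm imbalance and accounts for the starting value of the outcome, but it does not remove that confounding.

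Optional: section 1.1 states that "treatment with corticosteroids and immunosuppressants, as well as systemic inflammation, may also negatively impact on peripheral muscle function", and quadriceps strength is a secondary outcome, so corticosteroid and immunosuppressant use could be recorded in the same way. The point does not depend on it.

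Cost: one added data field, a few lines of wording and a weaker statement about antifibrotics. No visit or test is added.

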4 METHODS

4.1 STUDY DESIGN

This is a Randomized, Controlled, Multicentre Proof-of-Concept (PoC) Study of 30 patients with ILD, which will be randomized into 2 groups; the first group will be submitted to 8 weeks of a PR program based on HIIT plus HFNO and the second group will also be submitted to 8 weeks of a PR program based on HIIT, but with conventional oxygen delivery without HFNO. Which group will use HFNO or conventional oxygen will be randomly selected from a sealed envelope.

In general the study will consist of 8 weeks of intervention in the clinic plus 1 day of evaluations before and after the intervention. Spending 1 hour per day, three times a week every second day during the intervention and 2 hours during the other 2 days of evaluations approximately. The window between the baseline appointment and the first day of the intervention can be from 1 to 30 days, and the window between the last day of intervention and the post intervention appointment will be from 8 to 38 days. All the visits will take place in ward 204 (Respiratory Medicine) of the Royal Infirmary of Edinburgh (for participants from Edinburgh) and in the Royal Victoria Infirmary, Newcastle upon Tyne Hospital (for participants from Newcastle).

The following measurements will be conducted:

During the first day before of the intervention, a blood test will be taken (6 ml) to know the levels of blood biomarkers associated with fibrosis that have been shown to be associated with disease progression (Inc. but not restricted to PAI-1, VEGF-A, PDGF-AA, PDGF-BB, Cystatin-C, Angioprotein-1, HE4/WFDC-2). Additionally, a test called the quadriceps maximal voluntary contraction test (QMVCT) will be taken to measure the strength of the quadriceps muscle. The subjects are studied seated in a chair, with hip and knee flexion of 90 degrees. An inextensible strap is placed around the ankle, adjusted to ensure the knee remains at 90 degrees flexion. The ankle strap is connected to a strain gauge mounted on the back of the chair. A seatbelt is secured across the subject's hips to stabilise the pelvis. The patient has to do a knee extension and we can measure their strength.

Also, the shortness of breath will be assessed using the Modified version of the Medical Research Council scale (mMRC).

In addition, height and weight will be taken. Breathing tests will not be performed, because these procedures the participants have already done in the outpatient clinic.

In addition, a Cardiopulmonary Exercise Test (CPET) will be carried out.

Furthermore, a Constant work rate Cycle Test at 75% of peak work rate (obtained from a maximal exercise test conducted beforehand) will be carried out. The participants will be able to rest for about 20 minutes between each test and we will offer them refreshments.

Physical activity levels in daily life will also be measured using Actigraph GT3x activity monitor, which will be delivered during the baseline appointment to use in their house for only 1 week before and 1 week after of the intervention, this is a belt that the participants will have to use like any other. After of the intervention they should return it to us during their post intervention appointment.

Moreover, two questionnaires called St George's Respiratory Questionnaire (SGRQ) and the Hospital Anxiety and Depression Scale (HADS), will have to be answered to measure the quality of life and anxiety and depression levels respectively. These test will be answered at home.

During the first day after of the intervention, participants will be undergone exactly to the same tests as in the baseline appointment, except height.

Intervention, a group of participants will be submitted to 8 weeks of a PR program based on HIIT plus HFNO and the other group will also be submitted to 8 weeks of a PR program based on HIIT but with conventional oxygen delivery without HFNO. Both HIIT will be performed at the same workload, which will be progressive throughout the 8 weeks and will be modified during each session. Starting with high load intervals at 60% of the maximal watts achieved beforehand during a maximal CPET divided by lower load intervals at 40% maximum load during the first week, and finishing with high load intervals at 110% maximum load separated by load intervals at 80% maximum load in the last weeks. Basically the participants will have to pedal in a stationary bicycle for 30 minutes (aerobic training), during the other 20 minutes the patients will do exercises for their upper limbs using Thera bands and dumbbells (strength training). Muscles of upper limbs to work will be deltoids, pectorals and biceps (3 series of 10 repetitions each). Finally the participants will receive 10 minutes of respiratory physiotherapy including techniques to eliminate phlegm, breathing exercises and ludic activities to train the respiratory muscles such as inflating balloons.

Which group will use HFNO or conventional oxygen will be randomly selected from a sealed envelope. Randomized means that all participants will have the same chance of belonging to one group or another, they must choose a sealed envelope and inside it will be written to which group they will belong.

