4.2 NUMBER OF PARTICIPANTS

15 participants with ILD will be recruited in the Lothian region, and another 15 participants in the Royal Victoria Infirmary, Newcastle upon Tyne Hospital (for

10

participants from Newcastle). The length of recruitment period will be approximately 6 months.

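### The protocol gives two incompatible allocation procedures, a prepared sequence and a participant's free choice of envelope, and the second leaves no order of use that can be checked

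*Protocol*

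**What the plan says.** Protocol section 4.8 describes allocation by sealed letters. It takes place "Following confirmation of eligibility by the CI or PI and signature of the informed consent", and it adds "Patients will be sequentially randomised". On preparation it says "Randomisation code and sealing of envelopes will be done by the research nurses". The envelopes are kept in a room at the Royal Infirmary of Edinburgh and the Royal "Victoria Infirmary accessible with a key", and no key holder is named. The section places this step before any baseline procedure, and the schedule in 4.11 agrees by listing randomisation under screening.

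Sections 4.1 and 4.10 describe something else. Both explain randomisation by saying that "all participants will have the same chance of belonging to one group or another", and then that "they must choose a sealed envelope and inside it will be written to which group they will belong".

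Section 4.2 sets the site numbers: "15 participants with ILD will be recruited in the Lothian region, and another 15 participants in the Royal Victoria Infirmary". Section 4.9 makes the trial open label. Section 3.1 makes endurance time on a constant work rate cycle test the primary outcome. The protocol does not mention envelope numbering, opacity or an opening log, and it does not say how many envelopes of each kind are made.

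**The concern.** A prepared code used in sequence fixes which allocation comes next. A participant choosing among envelopes discards that order. Both cannot be followed, and two sites could each comply with the protocol while allocating differently.

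What is at stake is concealment and the evidence for it. If the envelope is chosen, the order of use cannot be compared with the code, so an envelope opened and put back would leave no trace. Three features of the design make this matter:

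- Past allocations are visible to staff, because the trial is open label.
- Allocation is fixed before baseline tests are done, so knowledge of it could affect both who is entered and how baseline is measured.
- The primary outcome depends on effort, and Appendix B has staff urge the patient on during the test.

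No later analysis can repair allocation that was not concealed.

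**Working it through.** **Comparing the sections**

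| Element | Section 4.8 | Sections 4.1 and 4.10 |
|---|---|---|
| What determines the allocation | Prepared code, used sequentially | Envelope the participant picks |
| Can order of use be checked against the code? | Yes, if envelopes are numbered and logged (neither is stated) | No |
| Who prepares | Research nurses | Not stated |

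The choice wording appears in two sections, so it is not a stray phrase.

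**Who does what.** The direct care team invites patients (4.5). The CI or PI confirms eligibility (4.8). Outcome data are collected by the CI and PI in Edinburgh and by a physiotherapist in Newcastle (4.12.2). No section gives the research nurses any of these tasks, and none rules them out.

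**Balance between sites.** The protocol states no figure to reproduce. The inputs are 15 patients per site (4.2) and an equal chance of either arm (4.1). Envelope composition is not given, so three assumptions show the range.

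*Simple 1:1.*
- One site at 11:4 or worse: 2 × (1 + 15 + 105 + 455 + 1365)/2^15 = 3882/32768 = 0.1185.
- At least one of two sites: 1 − (1 − 0.1185)² = 0.223.
- The same steps for 10:5 or worse give 0.302 for one site and 0.512 for at least one.

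*One shared pool of 15 + 15, all used.*
- One site at 11:4 or worse: 2 × Σ C(15,k)²/C(30,15) for k = 11 to 15, which is 2 × 2,081,501/155,117,520 = 0.027.
- The other site mirrors it, so this is also the chance for at least one site.

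*A set of 8 + 7 at each site.*
- A completed site ends 8:7 or 7:8, so the chance of 11:4 or worse is 0.

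**Arm and site confounded.** This depends on how far the arms differ in site mix, not on the overall split: 4:11 at both sites would leave arm and site unrelated. Let a and b be the numbers at the two sites allocated to one arm. Under simple 1:1, sum C(15,a)C(15,b)/2^30 over all pairs where |a/(a+b) − (15−a)/(30−a−b)| reaches the threshold. A difference of 20 percentage points or more has probability 0.362; 30 points or more, 0.112.

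**Predictability of an 8:7 pile.** Assume that someone knows the composition, sees every past allocation at the site and always guesses the arm with more envelopes left.
- From an 8:8 pile, expected correct guesses are 8 + (4^8/C(16,8) − 1)/2 = 8 + (65536/12870 − 1)/2 = 10.05.
- The first of those guesses is right with probability 1/2 and leaves 8:7, so an 8:7 pile gives 10.05 − 0.50 = 9.55 of 15, or about 64%.
- The expected number of final allocations known with certainty is 8/(7+1) + 7/(8+1) = 1.78.
- Under simple 1:1 the guessing rate is 50%.

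**The case against.** The best defence is that the word sequentially in 4.8 may mean only that patients are randomised one after another as they enrol. Drawing from a mixed pile of sealed envelopes is also still random. Both points are fair. But on that reading the free choice is the whole procedure, and it still leaves no order to check.

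A reader might infer more than the documents support, in four ways:

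- **That site imbalance is likely.** This depends on a composition the protocol does not give. Holding envelopes at both hospitals is compatible with a balanced set at each. Imbalance and predictability are also alternatives: simple 1:1 gives the first without the second, and a fixed 8:7 set the reverse.
- **That an uneven overall split shows confounding with site.** It does not. The relevant quantity is the difference in site mix between arms.
- **That the nurses enrol patients, hold the key or work at the recruiting sites.** Section 4.8 says none of this, and it gives eligibility to the CI or PI. The nurses' independence is unstated, not contradicted.
- **That blocks, strata or a site term in the analysis are missing.** The protocol is silent on them, and they may stand in a statistical analysis plan or randomisation document that is not at hand.

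None of these touches the conflict between 4.8 and sections 4.1 and 4.10. Another document could add blocks or strata, but it could not make the two procedures agree.

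**Conclusion.** The contradiction is real and should be removed before the first allocation. The choice procedure, followed as written, leaves no auditable sequence in an open-label trial that randomises before baseline and has an effort-dependent outcome. This conclusion rests on the text alone and needs no numerical assumption.

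The size of any site imbalance is secondary and conditional. At least one site at 11:4 or worse has probability 22% under simple 1:1, about 3% with a shared 15 + 15 pool and 0% with 8:7 per site. Imbalance is therefore possible, not likely. The roughly 64% guessing rate applies only to a fixed 8:7 pile of known composition with used envelopes tracked.

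**What to change.** In 4.1 and 4.10, delete the clause "they must choose a sealed envelope and inside it will be written to which group they will belong" and refer to 4.8.

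In 4.8, state one procedure:
- Use sequentially numbered opaque envelopes, or web allocation.
- Open them in order, after the patient's study ID is written on the envelope.
- Log each opening with date and time.
- Have the list made by someone who does not enrol, treat or test, and say so.

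While 4.8 is being rewritten, generate the list separately by site with varied block sizes that site staff do not know. This limits imbalance without creating a guessable pile. Because 15 is odd, exact equality within a site is impossible; the cost is at most one patient per site.

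The change costs amendment wording and a few hours of existing staff time. It adds no visit or test.
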